10.5 Appendix 5: Genetics

Use/Analysis of DNA

Genetic variation may impact a patient's response to therapy. Variable response to therapy may be due to genetic determinants that impact intervention absorption, distribution, metabolism, and excretion; mechanism of action of the intervention; disease etiology; and/or molecular subtype of the disease being treated. Therefore, where local regulations and IRB allow, a blood sample will be collected for DNA analysis.

DNA samples will be used for research related to TCK-276 or RA and related diseases. They may also be used to develop tests/assays related to study intervention and/or interventions of this drug class and RA. Genetic research may consist of the analysis of one or more candidate genes or the analysis of genetic markers throughout the genome or analysis of the entire genome (as appropriate) in relation to TCK-276 (as appropriate).

The samples may be analyzed as part of a multi-study assessment of genetic factors involved in the response to TCK-276 or study intervention of this class to understand the study disease or related conditions.

The results of genetic analyses may be reported in the CSR or in a separate study summary.

The Sponsor will store the DNA samples in a secure storage space with adequate measures to protect confidentiality.

10.6 [REDACTED]

[REDACTED]

[REDACTED]

[figure not shown]
[REDACTED]

[figure not shown]
[REDACTED]

[figure not shown]
[REDACTED]

[figure not shown]
[REDACTED]

Prohibited or cautioned medications may include, but are not limited to, those listed below. These listings of prohibited or cautioned concomitant treatments are not considered all inclusive.

10.7 Appendix 7: Abbreviations and Definitions

Abbreviations	Definition
ACR	American College of Rheumatology
AE	Adverse event
AESI	Adverse event of special interest
A_e	Amount of study drug excreted unchanged in the urine
ALT	Alanine aminotransferase
AST	Aspartate aminotransferase
AUC	Area under the plasma concentration-time curve
$AUC_{0-\infty}$	Area under the plasma concentration-time curve from pre-dose (time 0) extrapolated to infinite time ($AUC_{last} + Clast/\lambda_z$) calculated using the linear-log trapezoidal rule
AUC_{0-t}	Area under the plasma concentration-time curve up to last measurable concentration
AUC_{0-24h}	Area under the plasma concentration-time curve up to 24 hours
AUC_{τ}	Area under the plasma concentration-time curve over a dosing interval, $\tau = 24$ hours
[REDACTED]	[REDACTED]
BMI	Body mass index
BP	Blood pressure
bpm	Beats per minute
CCL2	C-C motif chemokine ligand 2
CDAI	Clinical disease activity index
CDK	Cyclin dependent kinase
CFR	Code of Federal Regulations
CL/F	Apparent total body clearance
CL_r	Renal clearance
C_{max}	Maximum plasma concentration determined directly from the concentration-time profile
COMP	Cartilage oligomeric matrix protein
COVID-19	Coronavirus disease 2019
CRF	Case report forms
CRO	Contract research organization
CSR	Clinical study report

Abbreviations	Definition
MRT _{last}	Mean residence time up to last measurable concentration
MRT _{0-inf}	Mean residence time extrapolated to infinity
NOAEL	No observed adverse effect level
[REDACTED]	[REDACTED]
[REDACTED]	[REDACTED]
OTC	Over-the-counter
PD	Pharmacodynamics
[REDACTED]	[REDACTED]
PK	Pharmacokinetics
PO	By mouth
PT	Preferred term
QD	Once daily
QTc	QT interval corrected for heart rate
QTcF	QT interval corrected for heart rate using Fridericia's correction
RA	Rheumatoid arthritis
RASF	Rheumatoid arthritis synovial fibroblasts
Rb	Retinoblastoma protein
SAD	Single ascending dose
SAE	Serious adverse event
SAP	Statistical analysis plan
SARS-CoV-2	Severe acute respiratory syndrome coronavirus 2
SC	Subcutaneous
SDAI	Simplified disease activity index
SoA	Schedule of Activities
SOC	System Organ Class
SOP	Standard operating procedure
SRC	Safety Review Committee
SUSAR	Suspected unexpected serious adverse reactions
t _{max}	Time of maximum plasma concentration determined directly from the concentration-time profile
TNF	Tumor necrosis factor
t _½	Terminal elimination half-life calculated

Abbreviations	Definition
ULN	Upper limit of normal

1.1		Updated dose strength to 175 mg throughout the document Update the unit of CRP from mg/dL to mg/L, accordingly, SDAI = SJC + TJC +PGA + EGA + 0.1*CRP DAS 28 CRP = $0.56 \times \checkmark$ (TJC) + $0.28 \times \checkmark$ (SJC) + $0.36 \times LN((CRP)+1) + 0.14* \times (PGA) + 0.96$ Added line in section 4.13.8 "If any of the elements are missing, then the corresponding parameter will be considered as missing." to handle the parameter in case of missing elements. Removed inactive URL link of DAS28 ESR	
20	Date of last signature	Final	

LIST OF ABBREVIATIONS

Abbreviation/Acronym	Definition/Expansion	
ACR	American College of Rheumatology	
AE	Adverse event	
Ae	Amount of study drug excreted unchanged in the urine	
AESI	Adverse events of special interest	
ALT	Alanine aminotransferase	
AST	Aspartate aminotransferase	
AUC	Area under the curve	
AUC _{0-inf}	Area under the plasma concentration-time curve from pre- dose (time 0) extrapolated to infinite time	
AUC _{0-t}	Area under the plasma concentration-time curve up to last measurable concentration	
AUC _{tau}	Area under the plasma concentration-time curve over a dosing interval	
BDRM	Blinded data review meeting	
BL	Biostatistician Lead	
BLQ	Below the lower limit of quantification	
BMI	Body mass index	
BP	Blood pressure	
bpm	Beats per minute	
CCL2	C-C motif chemokine ligand 2	
CDAI	Clinical disease activity index	
CI	Confidence interval	
CL/F	Apparent total body clearance, determined for parent only	
Clast	Last observed quantifiable concentration at tlast	
CLr	Renal clearance of drug from plasma	
C _{max}	Maximum plasma concentration determined directly from the concentration-time profile	
COMP	Cartilage oligomeric matrix protein	
CPMS	Clinical Pharmacology, Modeling, and Simulation	

Abbreviation/Acronym	Definition/Expansion	
CS	Clinically significant	
CSR	Clinical Study Report	
Ctrough	Concentration in a dosing period defined as the pre-dose concentration of the day	
CTCAE	Common Terminology Criteria for Adverse Events	
CV	Coefficient of variation	
CXCL10	C-X-C motif chemokine ligand 10	
DAS28	Disease activity score 28	
DRM	Data Review Meeting	
ECG	Electrocardiogram	
eCRF	Electronic case report form	
EGA	Evaluator Global Assessment (Provider global score)	
EOS	End of study	
Fe	Percentage of study drug excreted unchanged in the urine	
Fe%	Urinary cumulative excretion as % of unchanged drug	
GM-CSF	Granulocyte macrophage colony stimulating factor	
HAQ	Health Assessment Questionnaire	
HBc	Hepatitis B core	
GM-CSF	Granulocyte macrophage colony stimulating factor	
HBsAg	Hepatitis B surface antigen	
HCV	Hepatitis C virus	
HIV	Human immunodeficiency virus	
HR	Heart rate	
ICF	Informed consent form	
IGRA-TB	Interferon gamma release assay for tuberculosis	
IL-6	Interleukin-6	
LLOQ	Lower limit of quantification	
MAD	Multiple ascending dose	
MedDRA	Medical Dictionary for Regulatory Activities	
MMP-3	Matrix metalloproteinase-3	

Abbreviation/Acronym	Definition/Expansion
MR	Molar metabolic ratio
MRT	Mean residence time
MRT _{last}	Mean residence time up to last measurable concentration
MRT _{0-inf}	Mean residence time extrapolated to infinity
NC	Not calculated
NCS	Not clinically significant
NR	Not reportable
NS	No sample
PCS	Potentially clinically significant
PD	Pharmacodynamic(s)
PGA	Patient Global Assessment(or Patient Global Score)
РК	Pharmacokinetic(s)
PKAS	Pharmacokinetic analysis set
PT	Preferred term
QD	Once daily
QTc	corrected QT interval
QTcB	QT corrected using Bazett's formula
QTcF	QT corrected using Fridericia's formula
RA	Rheumatoid arthritis
R _{acc}	Accumulation ratio
RAN	Randomized Analysis Set
RTF	Rich text format
SAD	Single ascending dose
SAE	Serious adverse event
SAF	Safety Population
SAP	Statistical Analysis Plan
SARS-CoV-2	Severe acute respiratory syndrome coronavirus 2
SBP	Systolic blood pressure
SD	Standard deviation
SDAI	Simplified disease activity index

Abbreviation/Acronym	Definition/Expansion	
SI	Standard international	
SJC	Swollen Joint Count	
SoA	Schedule of Assessment	
SOC	System Organ Class	
SOP	Standard operating procedure	
SRC	Safety Review Committee	
t _{1/2}	Terminal elimination half-life	
TEAE	Treatment-emergent adverse event	
TEMA	Treatment-emergent markedly abnormal	
TJC	Tender Joint Count	
t _{last}	Time of last observed quantifiable concentration	
t _{max}	Time of maximum plasma concentration determined directly from the concentration-time profile	
TNF	Tumor necrosis factor	
Vur	Measured volume of urine collected during each collection interval	
V _z /F	Apparent volume of distribution based on terminal phase, determined for parent only	
WHO-DD	World Health Organization - Drug Dictionary	
λ_z	Terminal elimination rate constant	

1 INTRODUCTION

This Statistical Analysis Plan (SAP) describes all planned analyses for the Clinical Study Report (CSR) of Study TCK-276-102, A Phase 1, Randomized, Placebo-controlled, Double-blind, Multiple Ascending Dose Study to Investigate Safety, Tolerability, and Pharmacokinetics of Oral Doses of TCK-276 in Patients with Rheumatoid Arthritis.

The content of this SAP is based on following study documents:

- Study TCK-276-102 protocol Final Version 3.0 12 Dec 2022.
- Electronic Case Report Form (eCRF) Version 27.0

This SAP will be finalized prior to database lock. Any changes after the finalization of this SAP will be documented in Statistical Method Modification Form.

2 STUDY OBJECTIVES

2.1 **Primary Objective(s)**

	Objectives		Endpoints
•	To evaluate the safety and tolerability of	• Saf	fety and tolerability endpoints:
	multiple oral doses of TCK 276 in patients	The fo	llowing safety and tolerability variables
	with rheumatoid arthritis (RA)	will be	e recorded at regular intervals during the
		study:	
		0	Vital signs measurements: supine blood
			pressure, pulse, body temperature, and
			respiratory rate
		0	Cardiac safety for arrythmias,
			abnormalities including PR interval,
			QRS interval, RR interval, QT interval,
			and QT interval corrected for heart rate
			(QTc) (Fridericia's correction [QTcF])
			as assessed by 12-lead
			electrocardiogram (ECG) and cardiac
			telemetry
		0	Incidence of laboratory abnormalities:
			hematology, clinical chemistry,
			coagulation, and urinalysis
		0	Incidence and severity of adverse event
			(AE) and adverse event of special
			interest (AESI) (i.e., gastrointestinal
			toxicity and pulmonary symptoms
			indicative of interstitial lung disease)
			assessments
		0	Physical examinations

2.2 Secondary Objective(s)

	Objectives	Endpoints
•	To evaluate pharmacokinetic (PK) of TCK-	PK endpoints
	276 and its metabolite (TEI-W00595) in	The following PK parameters for TCK-276 and
	patients with RA after multiple ascending	TEI-W00595 will be determined, if calculable:
	dose (MAD) administration	• C _{max} : Maximum plasma concentration
		determined directly from the
		concentration-time profile (Days 1 and
		7)
		o t _{max} : Time of maximum plasma
		concentration determined directly from
		the concentration-time profile (Days 1
		and 7)
		• AUC _{tau} : Area under the plasma
		concentration-time curve over a dosing
		interval, tau = 24 hours (Days 1 and 7)
		\circ AUC _{0-t} : Area under the plasma
		concentration-time curve up to last
		measurable concentration (Days 1 and 7)
		\circ AUC _{0-inf} : Area under the plasma
		concentration-time curve from pre-dose
		(time 0) extrapolated to infinite time
		(Days 1 and 7)
		• MRT _{last} : Mean residence time up to last
		measurable concentration (Day 1 only)
		• MRT _{0-inf} : Mean residence time
		extrapolated to infinity (Days 1 and 7)
		\circ t _{1/2} : Terminal elimination half-life (Days
		1 and 7)
		• CL/F: Apparent total body clearance
		(Days 1 and 7), determined for parent
		only
		\circ V _z /F: Apparent volume of distribution
		based on terminal phase (Days 1 and 7),
		determined for parent only
		\circ Metabolic ratio (MR) for C _{max} : Molar
		metabolic ratio of C _{max} calculated as
		$(C_{max} [metabolite] \times molecular weight of$
		parent)/(C_{max} [parent] × molecular
		weight of metabolite) (Days 1 and 7)
		• MR for area under the plasma
		concentration-time curve (AUC): Molar
		metabolic ratio of AUC calculated as
		(AUC [metabolite] × molecular weight
		of parent)/(AUC [parent] × molecular
		weight of metabolite) (Days 1 and 7)

Teijin America, Inc. TCK-276-102

• C _{trough} : Concentration in a dosing period
defined as the pre-dose concentration of
the day
\circ R _{acc} (C _{max}): Accumulation ratio based on
C_{max} : Calculated as C_{max} on Day 7/ C_{max}
on Day 1
\circ R _{acc} (AUC _{tau}): Accumulation ratio based
on AUC _{tau} : Calculated as AUC _{tau} on Day
$7/AUC_{tau}$ on Day 1
The following urinary PK parameters for TCK-
276 will be determined in this study:
• Ae: Amount of study drug excreted
unchanged in the urine (Days 1 and 7)
\circ F _e : Percentage of study drug excreted
unchanged in the urine (Days 1 and 7)
CL = D = 1 = 1 = 1 = 1 = 1 = 1
\circ CL _r : Kenal clearance (Days 1 and 7)
Other PK parameters will be determined if
needed.

2.3 Exploratory Objective(s)

 To evaluate the effect of TCK-276 on disease activity and biomarkers in patients with RA The par 	Exploratory endpoints he following exploratory disease activity arameters for RA will be assessed: • American College of Rheumatology (ACR) 20/50/70 response criteria • Disease activity score 28 (DAS28) • Clinical disease activity index (CDAI) • Simplified disease activity index (SDAI) he following exploratory biomarkers will be ssessed: • Matrix metalloproteinase-3 (MMP-3) • Granulocyte macrophage colony- stimulating factor (GM-CSF) • C-X-C motif chemokine ligand 10 (CXCL10) • C-C motif chemokine ligand 2 (CCL2) • Cartilage oligomeric matrix protein (COMP) • Tumor necrosis factor (TNF)-alpha • TNF-R1 • Interleukin-6 (IL-6)

3 INVESTIGATIONAL PLAN

3.1 Overall Study Design and Plan

This is a Phase 1, multi-center, double-blind, randomized, placebo-controlled, multiple ascending dose (MAD) study to evaluate the safety, tolerability, and pharmacokinetics (PK) of orally administered TCK-276 in both males and females with RA. Blood samples for possible future pharmacogenetic, possible future metabolite assessments, and possible future pharmacodynamic (PD) assessments will be collected.

A total of thirty-two (32) patients with RA will be enrolled in this clinical study. This MAD study will consist of 4 cohorts of 8 patients (6 active treatment and 2 matching placebo, or a 3:1 ratio), each receiving an oral dose of TCK-276 or matching placebo for 7 days (once daily [QD] under fed condition). Each cohort will be divided into 2 subgroups to implement the sentinel dosing approach. Within each cohort, the first subgroup will consist of 2 sentinel patients; one patient will receive TCK-276, and one patient will receive matching placebo. The second subgroup will consist of 6 patients (5 active treatment, 1 matching placebo). Individual patients in the second subgroup will be dosed at least 72 hours after the first subgroup following a decision by the Investigators based on all available safety data from the sentinel patients up to 48 hours post-dose.

Dose group	Treatment Assignment	
1	10 mg TCK-276 (N = 6)	Placebo $(N = 2)$
2	25 mg TCK-276 (N = 6)	Placebo $(N = 2)$
3	75 mg TCK-276 (N = 6)	Placebo $(N = 2)$
4	175 mg TCK-276 (N = 6)	Placebo $(N = 2)$

Patients will be admitted to the site from the morning of Day -1 and sequestered for the duration of the treatment (dosing) period. Each patient will receive QD oral doses of either TCK-276 or matching placebo administered as tablets under fed condition in the morning of Day 1 to Day 7. The patients will be discharged on Day 10. The planned dose levels to be tested are 10 mg (Cohort 1), 25 mg (Cohort 2), 75 mg (Cohort 3), and 175 mg (Cohort 4) of TCK-276. Based on the results from the SAD study (5 mg to 185 mg dosing) and the projected clinical effective dose (i.e., 75 mg), 10 mg is selected as the starting dose level in the MAD study. The dose in Cohorts 2, 3, and 4 may be adjusted based on the safety and PK results from the previous cohorts, if necessary. The overall exposure to TCK-276 (in terms of geometric mean area under the plasma concentration-time curve over a dosing interval [AUC_{tau}, tau = 24 hours]) on Day 7 would not be expected to exceed 2,355 ng·h/mL, which is set taking monkey testicular toxicity into consideration.

Dose escalation will only be allowed after blinded assessment of all safety, tolerability, and PK data up to Day 10 from each previous cohort evaluated by Investigators, Medical Monitor, and Sponsor representatives during the Safety Review Committee (SRC) meeting.

Max.

28 days

before

first dose

Day -1

Day 1

Day 2

C

Figure 3-1 Study Design

N = number of patients; PK = pharmacokinetics

Figure 3-2 Study Flow Chart – Multiple Ascending Dose Design

VISIT 1 VISIT 2 VISIT 3 Enrolment Treatment period Followup/End of treatment Informed Admission Randomization Multiple dose Discharge consent and dosing administration Screening period

Day 7

Days 8, 9

Day 10

Day 14

(7 days

after

last dose)

3.2 Endpoints and Associated Variables

3.2.1 Safety Variables

The following safety and tolerability variables will be recorded at regular intervals during the study:

- Vital signs (supine blood pressure [BP] and pulse rate, tympanic (ear) body temperature, respiratory rate)
- Cardiac safety for arrythmias, abnormalities including PR interval, QRS interval, RR interval, QT interval, and QT interval corrected for heart rate (QTc) (Fridericia's correction [QTcF]) as assessed by 12-lead electrocardiogram (ECG) and cardiac telemetry.
- Incidence of laboratory abnormalities: hematology, clinical chemistry, coagulation, and urinalysis
- Incidence and severity of adverse event (AE) and adverse event of special interest (AESI) (i.e., gastrointestinal toxicity and pulmonary symptoms indicative of interstitial lung disease) assessments
- Physical examinations

3.2.2 Pharmacokinetic Variables

Pharmacokinetic concentration data will be obtained at time point(s) described in the protocol version 2.0 as follows:

Blood sample for PK sample analysis to determine parent (TCK-276) and its metabolite (TEI-W00595) concentrations and for possible future metabolite assessments will be collected at the time points detailed in the Schedule of Assessments Each plasma sample will be divided into 4 aliquots (1 each for the PK, the possible future metabolite assessments, a backup for the PK, and a backup for the possible future metabolite assessments).

Blood for the PK sample analysis and for possible future metabolite assessments will be sampled at pre-dose and 0.25, 0.5, 1, 1.5, 2, 3, 4, 6, 8, 12, 16, and 24 hours (pre-dose of Day 2) after dosing on Day 1, pre-dose on Days 3, 4, 5, 6, and on 7, and 0.25, 0.5, 1, 1.5, 2, 3, 4, 6, 8, 12, 16, 24, 48, and 72 hours after dosing on Day 7. The sampling time points may be adjusted based on the PK results obtained from the previous cohorts. The last dose will be administered on Day 7.

Urine samples for the analysis of TCK-276 will be collected at the following time intervals relative to study drug dosing: 0 to 6 hours, 6 to 12 hours, 12 to 24 hours after dosing on Day 1, and from 0 (pre-dose) to 6, 6 to 12, 12 to 24, 24 to 48, and 48 to 72 hours after dosing on Day 7. Volumes of urine collected in each time window will also be recorded in the clinical database. Urine collection intervals may be adjusted based on the PK results obtained from the previous cohorts, e.g., if plasma PK sampling times are adjusted, the urine sampling times will be updated.

Derivation of PK parameters will be the responsibility of Clinical Pharmacology, Modeling and Simulation (CPMS) group,

If calculable, the following PK Day 1 parameters listed in Table 3-1 will be determined for parent, TCK-276 and metabolite, TEI-W00595, in plasma following first oral dose administration.

Parameter	WNL Name	CDISC Name	Definition
C _{max}	Cmax	CMAX	Maximum observed concentration determined directly from the concentration-time profile
DNC _{max}	CmaxD	CMAXD	Dose-normalized C _{max}
t _{max}	Tmax	TMAX	Time of maximum plasma concentration corresponding to occurrence of C_{max}
λ_z	Lambda_z	LAMZ	Terminal elimination rate constant
AUC _{tau}	AUC_TAU	AUCTAU	Since dosing interval or tau equals 24 hours, area under the curve from time 0 to 24 hours (AUC _{0-24h}) will be calculated and will be referred to AUC _{tau} for Day 1
DNAUC _{tau}	AUC_TAUD	AUCTAUD	Dose normalized AUC _{tau}
AUC _{0-t}	AUClast	AUCLST	AUC from time zero to the last quantifiable concentration
DNAUC _{0-t}	AUClast_D	AUCLSTD	Dose-normalized AUC _{0-t}
AUC _{0-inf}	AUCINF_obs	AUCIFO	AUC from time zero extrapolated to infinity
%AUC _{ex}	AUC_%Extrap_obs	AUCPEO	Percentage of AUC_{0-inf} obtained by extrapolation beyond t_{last}
DNAUC _{0-inf}	AUCINF_D_obs	AUCIFOD	Dose-normalized AUC _{0-inf}
MRT _{last}	MRT _{last}	MRTEVLST	Mean residence time up to last measurable concentration
MRT _{0-inf}	MRTINF_obs	MRTEVIFO	Mean residence time extrapolated to infinity

Table 3-1 Plasma Pharmacokinetic Parameters of TCK-276 and TEI-W00595 After First Dose Administration

CONFIDENTIAL

Teijin America, Inc. TCK-276-102

WNL **CDISC** Name Definition Parameter Name Apparent terminal elimination half-life $t_{\frac{1}{2}}$ HL Lambda z LAMZHL CL/F Cl F obs **CLFO** Apparent clearance following oral administration, determined for parent only V_z/F Vz_F_obs VZFO Apparent volume of distribution during terminal phase, determined for parent only Molar metabolic ratio based on Cmax of **MR**_{Cmax} MRCmax MRCMAX parent and metabolite MR_{AUCtau} **MRAUCtau** MRAUC Molar metabolic ratio based on AUC_{tau} of parent and metabolite MRAUClast MRAUCLS Molar metabolic ratio based on AUC_{0-t} MRAUC0-t of parent and metabolite **MRAUCINF MRAUCIN** Molar metabolic ratio based on AUC_{0-inf} MR_{AUC0-inf} of parent and metabolite

If calculable, the PK Day 7 parameters listed in Table 3-2 will be calculated for parent, TCK-276 and metabolite, TEI-W00595 in plasma following once daily oral dose administration after last dose administration on Day 7:

Parameter	WNL Name	CDISC Name	Definition
C _{max}	Cmax	CMAX	Maximum observed concentration determined directly from the concentration-time profile
DNC _{max}	CmaxD	CMAXD	Dose-normalized C _{max}
t _{max}	Tmax	TMAX	Time of maximum plasma concentration corresponding to occurrence of C_{max}
λ_z	Lambda_z	LAMZ	Terminal elimination rate constant
AUC _{tau}	AUC_TAU	AUCTAU	Since dosing interval or tau equals 24 hours, area under the curve from time 0 to 24 hours (AUC _{0-24h}) will be calculated and will be referred to AUC _{tau} for Day 7
DNAUCtau	AUC_TAUD	AUCTAUD	Dose-normalized AUCtau
AUC _{0-t}	AUClast	AUCLST	AUC from time zero to the last quantifiable concentration
DNAUC _{0-t}	AUClast_D	AUCLSTD	Dose-normalized AUC _{0-t}
AUC_{0-inf}	AUCINF_obs	AUCIFO	AUC from time zero extrapolated to infinity
%AUC _{ex}	AUC_%Extrap_obs	AUCPEO	Percentage of AUC_{0-inf} obtained by extrapolation beyond t_{last}
DNAUC _{0-inf}	AUCINF_D_obs	AUCIFOD	Dose-normalized AUC _{0-inf}
MRT _{0-inf}	MRTINF_obs	MRTEVIFO	Mean residence time extrapolated to infinity
t½	HL_Lambda_z	LAMZHL	Apparent terminal elimination half-life
CL/F	Cl_F_obs	CLFO	Apparent clearance following oral administration, determined for parent only

Table 3-2 Plasma Pharmacokinetic Parameters of TCK-276 and TEI-W00595 After Last Dose of Daily Dose Administration

Teijin America, Inc. TCK-276-102

Statistical Analysis Plan

Parameter	WNL Name	CDISC Name	Definition
V _z /F	Vz_F_obs	VZFO	Apparent volume of distribution during terminal phase, determined for parent only
MR _{Cmax}	MRCmax	MRCMAX	Molar metabolic ratio based on C_{max} of parent and metabolite
MRAUCtau	MRCAUCtau	MRCAUC	Molar metabolic ratio based on AUC_{tau} of parent and metabolite
MR _{AUC0-t}	MRAUClast	MRAUCLS	Molar metabolic ratio based on AUC_{0-t} of parent and metabolite
$MR_{\rm AUC0\text{-}inf}$	MRAUCINF	MRAUCIN	Molar metabolic ratio based on AUC _{0-inf} of parent and metabolite
Ctrough	Ctrough	CTROUGH	Concentration in a dosing period defined as pre-dose concentration of the day on Day 2 to Day 7, and 24 after Day 7 dosing
$R_{acc}(C_{max})$	ARCMAX	ARCMAX	Accumulation ratio based on C_{max}
$R_{acc}(AUC_{tau})$	ARAUC	ARAUC	Accumulation ratio based on AUC _{tau}

Additional PK parameters will be determined and reported as needed.

The concentration of TCK-276 as well as volume of urine collected in each collection interval (V_{ur}) will be used to calculate amount of TCK-276 in each collection interval and to determine the urine PK parameters listed in Table 3-3.

Protocol Parameter	WNL Name	CDISC Name	Definition
Ae	Amount Recovered	RCAMINT	Amount of unchanged drug excreted in urine in each interval collection (e.g. Ae ₀₋₆ , Ae ₆₋₁₂ , Ae ₁₂₋₂₄ after Day 1 and Day 7 dosing, additionally Ae ₂₄₋₄₈ and Ae ₄₈₋₇₂ following Day 7 dosing). In addition, cumulative amount excreted after each collection interval will also be determined (e.g. Ae ₀₋₆ , Ae ₀₋₁₂ , Ae ₀₋₂₄ after Day 1 and Day 7 dosing, additionally Ae ₀₋₄₈ and Ae ₀₋₇₂ following Day 7 dosing)
Fe	Percent_Recovered	RCPCINT	Urinary cumulative excretion as % of unchanged drug up to 24 hours following Day 1 and Day 7 dosing, and additionally up to 72 hours following Day 7 dosing (e.g. Fe ₀₋₆ , Fe ₀₋₁₂ , Fe ₀₋₂₄ after Day 1 and Day 7 dosing, additionally Fe ₀₋₄₈ and Fe ₀₋₇₂ following Day 7 dosing).
CLr	CLR@	RENALCL	Renal clearance of the drug from plasma following Day 1 and Day 7 dosing

Table 3-3 Urine Pharmacokinetic Parameters

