4.12.2 Pharmacokinetic Parameters

PK parameters will be provided by CPMS group. PK parameters will be calculated by NCA methods from the concentration-time data using Phoenix[®] WinNonlin[®] Version 8.3 or higher following these guidelines:

- Actual time from dose will be used in the calculation of all derived pharmacokinetic parameters, except when parameters are calculated for safety/dose escalation meetings when nominal times may be used to calculate PK parameters.
- There will be no imputation of missing data.
- Handling of BLQ samples for derivation of plasma PK parameters after multiple dose administration
 - BLQs for Day 1 at the beginning of a patient profile (i.e., before the first incidence of a measurable concentration) will be assigned to zero
 - BLQs on subsequent dosing days, and BLQs in the absorption phase will be substituted by zero before the calculation of the PK parameters
 - BLQ values between non-BLQ concentrations will be considered missing
 - \circ Terminal BLQs (at the end of patient profile) will be set to missing
- If urinary concentration is BLQ or if urine volume is not collected, amount of unchanged drug recovered in urine (A_e) will be defined as NC

Pharmacokinetic parameters will be estimated according to the guidelines presented in Table 4-1.

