	considers the reported values to be anomalous. Any data points so designated		
	should remain in the listings with a footnote and be identified in the study report		
	with a rationale for exclusion.		
CI /F	Apparent clearance after 1 st dose will be calculated as follows:		
CL/I	$CL/F = \frac{Dose}{AUC_{0-inf}}$		
	Apparent clearance (CL/F) following oral dosing will be calculated similarly for Day 7 where AUC_{tau} will be the denominator, assuming steady state has been achieved then.		

Parameter	Guideline for Derivation	
MRT _{last}	MRT _{last} will be calculated as follows: MRT _{last} = AUMC _{last} /AUC _{last} (Day 1 only)	
MRT _{0-inf}	MRT _{0-inf} will be calculated as follows:	
	Day 1: AUMC _{0-inf} /AUC _{0-inf}	
	Day 7: $(AUMC_{tau} + \tau^*(AUC_{0-inf} - AUC_{tau})) / AUC_{tau}$	
	Where AUMC is the area under the moments curve and τ is the dosing interval.	
V _z /F	Volume of distribution at terminal phase on Day 1 will be calculated as follows:	
	$V_z/F = \frac{Dose}{\lambda_z \times AUC_{0-inf}} = (CL/F)/\lambda_z$	
	Likewise, if derived for Day 7 or steady, AUC_{tau} will be used.	
CLr	Renal clearance will be calculated from the ratio of the appropriate values for urinary recovery and area under the concentration-time curve, where x will be 24 (Day 1) and 72 (Day 7) hours:	
	$CL_r = \frac{Ae_{(0-x)}}{AUC_{(0-x)}}$	
R _{acc}	Accumulation ratio, calculated from comparison of single dose (Day 1) and steady state (Day 7) data:	
	$R_{acc}(AUC_{tau}) = \frac{Steady \ state \ AUC_{tau}}{Single \ dose \ AUC_{tau}}$	
	$R_{acc}(C_{max}) = Steady \ state \ C_{max} / Single \ dose \ C_{max}$	
A _e	Amount of unchanged drug recovered in urine is calculated as	
	$A_e = Urine \ drug \ concentration \ * \ urine \ volume$	
	This is calculated for each urine collection interval and then summed for the cumulative A_{e} .	
Fe%	The percent of drug recovered in urine is calculated as	
	$F_e = 100 * A_e/Dose$	
	This is calculated for each urine collection interval and then summed for the cumulative $F_e\%$.	
MR for AUC	Metabolite molar ratio for Day 1 and Day 7 will be calculated as	
	MR for $AUC_{0-inf} = (AUC_{0-inf} metabolite/AUC_{0-inf} parent) * (MW parent/MW metabolite)$	
	Similarly, metabolite molar ratios will be collected for other AUCs defined earlier in this SAP.	
	Metabolite molar ratios will be calculated based on molecular weight of parent, TCK-276 and for metabolite TEI-W00595.	

Parameter	Guideline for Derivation

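### Day 7 Fe0-48 and Fe0-72 include residual drug from doses 1–6 but divide by one dose, so they overstate the percentage of a dose excreted unchanged

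*SAP*

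**What the plan says.** The protocol lists Ae, Fe and CLr on Days 1 and 7 among the secondary PK endpoints (Table 3-1). Seven once-daily doses are given, and seven days are taken as long enough to reach steady state (Protocol 4.3). Urine is collected to 24 h after dose 1 and to 72 h after dose 7, with each interval's volume recorded (SAP 3.2.2).

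SAP Table 3-3 defines Fe cumulatively to 24 h on both days "and additionally up to 72 hours following Day 7 dosing", naming Fe0-48 and Fe0-72. Table 4-1 gives Fe = 100 × Ae/Dose and adds: "This is calculated for each urine collection interval and then summed for the cumulative" value. There is no separate Day 7 form of Fe. CL/F does have one: on Day 7, AUCtau "will be the denominator, assuming steady state has been achieved then". Vz/F and MRT0-inf also have Day 7 forms based on AUCtau. The parameter figures in SAP 4.12.2 plot cumulative percentage excreted against collection end time for Day 7, individually and as means.

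On urine below the limit of quantification, SAP 4.12.2 says: "If urinary concentration is BLQ or if urine volume is not collected, amount of unchanged drug recovered in urine" is set to NC. The same list states: "There will be no imputation of missing data".

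**The concern.** After dose 7 the urine contains that dose's excretion plus what remains of the six before it, yet the divisor is one dose. Over exactly one dosing interval at steady state these balance: the residual drug coming in equals the part of dose 7 still to be excreted. Beyond 24 h no new dose is given, the numerator keeps growing and the balance is lost. A reader of the Day 7 curve would take its 72 h endpoint as the percentage of a dose excreted unchanged, and it would be too high.

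The secondary issue is the treatment of BLQ urine. With a recorded volume, the amount in a BLQ interval lies between 0 and LLOQ × volume. With no volume it is unknown. The SAP gives both the same result, NC, and does not say what happens when an NC term enters the sum.

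**Working it through.** The documents state no numerical Fe, half-life, urine LLOQ or BLQ rate, so there is no plan figure to reproduce.

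**Carry-over.** Inputs from the documents: 7 doses, 24 h apart, with windows to 24, 48 and 72 h after dose 7. Let f(t) be the share of one dose's eventual urinary excretion that has appeared t hours after that dose. By linear superposition, the amount excreted over 0–x h after dose 7, relative to one dose's total, is the sum over j = 0 to 6 of f(24j + x) − f(24j). This telescopes:

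- 0–24 h: f(168)
- 0–48 h: f(168) + f(192) − f(24)
- 0–72 h: f(168) + f(192) + f(216) − f(24) − f(48)

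If a dose is essentially cleared within seven days, the ratios are 1, 2 − f(24) and 3 − f(24) − f(48). The 72 h excess is the part of a dose still unexcreted at 24 h plus the part unexcreted at 48 h. The direction needs only linearity and near-steady state.

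For size, assume one compartment with oral input: f(t) = 1 − (ka·e^(−kt) − k·e^(−ka·t))/(ka − k), k = ln 2/t½. Example with t½ 12 h and ka 1/h: f(24) = 0.7347, f(48) = 0.9337, f(168) = 0.9999. The ratios are 1.000, 1.265 and 1.332.

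Over ka 0.3–1/h:

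| t½ (h) | Fe0-24 ratio | Fe0-48 ratio | Fe0-72 ratio | Fe0-72 excess | Doses 1–6 share of Ae0-72 | 48–72 h share of Ae0-72 |
|---|---|---|---|---|---|---|
| 4 | 1.00 | 1.019–1.036 | 1.019–1.037 | 2–4% | 2–4% | under 0.1% |
| 8 | 1.00 | 1.137–1.176 | 1.154–1.197 | 15–20% | 14–17% | 1.5–1.8% |
| 12 | 1.00 | 1.265–1.309 | 1.332–1.387 | 33–39% | 26–29% | 5.0–5.6% |
| 24 | 0.99 | 1.503–1.540 | 1.758–1.815 | 76–81% | 50–53% | 14.5–15.1% |

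**Which half-lives are plausible.** Day 1 plasma sampling stops at 24 h, yet Table 3-1 plans Day 1 AUC0-inf and t½. Table 4-1 excludes such values from summaries when more than 30% of AUC is extrapolated, or when the λz window is under 1.3 half-lives, unless the PK scientist or sponsor decides otherwise. In the same model the extrapolated share is 1 − f(24): 14–18% at 8 h, 27–31% at 12 h, 37–41% at 16 h and 51–55% at 24 h. A 24 h profile cannot hold 1.3 half-lives once t½ exceeds 24/1.3 = 18.5 h.

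**BLQ urine.** If NC propagates through the sum, a BLQ at 48–72 h removes Ae0-72, Fe0-72 and Day 7 CLr, which uses Ae to 72 h. The 0–24 and 0–48 h values survive. SAP 4.12.2 gives no statistics for fewer than three values. With 6 active patients and an assumed BLQ rate of 20%, 50% or 80% at 48–72 h, the chance that fewer than 3 keep Ae0-72 is 2%, 34% or 90% (at 50%: (1 + 6 + 15)/64 = 0.344).

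**The case against.** The strongest reply is that the valid quantity is already planned. Day 7 Fe0-24 is in Table 3-3 and meets the protocol endpoint. Fe0-48 and Fe0-72 are extra descriptive values, labelled as following Day 7 dosing. This stands as a limit on the harm, but nothing in the SAP tells a reader that the later values include earlier doses.

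The second reply is that the large errors need long half-lives, and a sponsor holding single-dose PK data would hardly plan Day 1 parameters that its own rules would mostly discard. That is fair as inference, though the Day 1 parameters are planned only if calculable. The 24 h row should carry little weight. The two problems also pull apart: a long half-life enlarges the carry-over and makes late BLQ urine less likely, so the harms should not be added together.

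Two stronger readings are tempting:

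- *One BLQ interval voids all cumulative results.* The SAP sets only the interval amount to NC and is silent on the sum. A program that skipped NC would in effect count it as zero. Even under propagation, only windows containing that interval are lost.
- *The Day 7 CLr definition is wrong.* Table 4-1 specifies Ae(0-x)/AUC(0-x), "where x will be 24 (Day 1) and 72 (Day 7) hours". Residual drug is in both numerator and denominator, so carry-over does not bias it. Table 3-2 has no AUC0-72, and its AUC0-t is the "AUC from time zero to the last quantifiable concentration". But Table 4-1 itself calls for the 72 h window, and SAP 3.2.2 allows additional parameters. The plasma rule, "Terminal BLQs (at the end of patient profile) will be set to missing", could shorten the AUC, but a mismatch needs quantifiable 48–72 h urine together with BLQ 72 h plasma. The documents give no basis for assuming that.

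**Conclusion.** The carry-over point holds. As written, Day 7 Fe0-48, Fe0-72 and the Day 7 percentage figures beyond 24 h overstate the per-dose fraction excreted unchanged, while Fe0-24 is essentially correct. Under the assumed model the Fe0-72 excess is slight at a 4 h half-life and about a third at 12 h. Larger values are arithmetically possible but less credible here. The sizes rest on linear kinetics, complete collection and an assumed half-life and absorption rate; the direction does not depend on the compartment model.

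The BLQ point holds as an ambiguity to be settled, not as a stated rule that destroys data. The CLr definition is not at fault. Urine PK is descriptive and no hypothesis is tested, so the effect is confined to how these secondary results are reported.

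**What to change.** 1. In Tables 3-3 and 4-1, make Fe0-24 the Day 7 Fe. Report 24–48 h and 48–72 h as amounts (Ae) only.
2. End the Day 7 percentage figures at 24 h, or footnote later points as including drug from earlier doses.
3. State how NC enters the sum. For cumulative Ae, count a BLQ interval of recorded volume as 0, list LLOQ × volume as its upper bound, and footnote that the interval value itself is shown as NC. Set the cumulative value to NC only when a volume or sample is missing. If every interval in a window is BLQ, report the total as below its bound, and omit geometric statistics from any summary containing zeros.

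Ae0-24/AUCtau is an optional alternative for Day 7 CLr, matching the Day 1 window. It discards the 24–72 h urine, which is 25–28% of Ae0-72 at a 12 h half-life.

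The cost is a few SAP sentences, a footnote and minor programming, with no new data. Since the SAP is final, SAP section 1 would place the change in its modification form. The footnote in item 3 is needed because cumulative values will no longer be a plain sum of the listed intervals.

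The drawback is understatement by up to LLOQ × volume per BLQ interval. For an assumed LLOQ of 10 ng/mL, 2000 mL and 1% excreted, that is 0.02 mg. It is 20% of the 0.1 mg expected at 10 mg and 2.7% of the 0.75 mg expected at 75 mg. With 1 ng/mL, 500 mL and 10% excreted it is 0.05% at 10 mg. It could therefore matter at the lowest dose, which is why the bound must be listed.
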